## Method

### Study design

The study is designed as a Phase 1/2a single-centre, double-blind, dose escalation, age de-escalation trial in malaria-exposed Malian adults and children. Two sequential stages of clinical research are conducted, each recruiting a distinct cohort of participants to confirm: 1. TB31F safety and 2. TB31F efficacy. Pharmacokinetic measurements will be performed in both safety and efficacy cohorts.

In total, a minimum of 165 participants will be recruited and enrolled; 45 adults and 30 children for the safety study, and ≥ 90 adults and children for the efficacy study. In the tables below, the cohorts are described with the number of participants, the duration of follow-up and the dose of TB31F administered.

*Table 1. Study design for Cohort 1 (Adults): Safety and pharmacokinetics (18-50 years of age)*

Group	Dose	N	Volume TB31F/Saline	Sample timepoints*	Safety follow-up after each dose administration
1	1A: Control (normal saline)	5	0.2 mL	Day 0 (Baseline), 1, 5, 7, 14, 21, 28, 42, 56, 84	Solicited local and systemic AEs (days 1-7); Unsolicited AEs (study duration); SAEs (study duration)
	1B: 10 mg mAb TB31F	10			
2	2A: Control (normal saline)	5	2 mL		
	2B: 100 mg mAb TB31F	10			
3	3A: Control (normal saline)	5	4 mL		
	3B: 200 mg mAb TB31F	10			

\* Group 1 participants will be followed-up until day 28

*Table 2. Study design for Cohort 1 (Children): Safety and pharmacokinetics in school age children (>10-15 years)*

Group	Dose	N	Volume TB31F/Saline	Sample timepoints	Safety follow-up after each dose administration
4	4A: Control (normal saline)	5	0.2 mL	Day 0 (Baseline), 1, 5, 7, 14, 21, 28, 42, 56, 84	Solicited local and systemic AEs (days 1-7); Unsolicited AEs (study duration); SAEs (study duration)
	4B: 10 mg mAb TB31F	10			
5	5A: Control (normal saline)	5	2.0 mL		
	5B: 100 mg mAb TB31F	10			

*Table 3. Study design for Cohort 2: Efficacy in a mixed age cohort (>10-50 years of age)*

Group	Dose	N	Volume TB31F/Saline	Sample timepoints	Safety follow-up after each dose administration
6.1	6AB: Control (normal saline)	15	0.6* mL	Day 0 (Baseline), 1, 5, 14, 21, 28, 56, 84	Solicited local and systemic AEs (days 1-7); Unsolicited AEs (study duration); SAEs (study duration)
	6B: 30 mg mAb TB31F	30	0.6* mL		
6.2	6AC: Control (normal saline)	15	2.0 mL		
	6C: 100 mg mAb TB31F	30	2.0 mL		

AE = Adverse events, SAE = Serious adverse events. Participants will be randomised in a 1:2:1:2 ratio to the 6AB, 6B, 6AC, or 6C group.

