#### Statistical Principles

##### Confidence intervals and P values

Confidence intervals and P values will be based on 0.05 as significance level. Adjustments for multiple comparisons will be implemented where appropriate but not for pre-defined study endpoints.

Where applicable, normally distributed continuous outcomes will be presented as mean with 95% CI or standard deviations. Continuous outcomes that are not normally distributed will be transformed using

a suitable transformation before reporting 95% CIs. Where a suitable transformation cannot be found, medians will be presented with interquartile ranges. For discrete (or count) data we will find interquartile ranges. Binary data will be presented as counts and proportions.

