#### Efficacy outcome measures related to within-group % reduction in proportion infected mosquitoes:

8. Group averaged within-individual percent reduction in the proportion of mosquitoes infected at day 5 post-treatment relative to baseline (day 0), assessed through direct membrane feeding assays (DMFA) and measured as oocyst prevalence (timeframe: day 0 [baseline] & 5)
9. Group averaged within-individual percent reduction in the proportion of mosquitoes infected in DSF, at all feeding timepoints relative to baseline (day 0). Comparisons of these reductions between groups at each post-baseline timepoint and comparisons of the reductions between post-baseline timepoints for each group (timeframe: day 0 [baseline], 1, and 5)
10. Group averaged within-individual percent reduction in the proportion of mosquitoes infected in DMFA, at all feeding timepoints relative to baseline (day 0). Comparisons of these reductions between groups at each post-baseline timepoint and comparisons of the reductions between post-baseline timepoints for each group (timeframe: day 0 [baseline], 1, 5, and 14)

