TRA and TBA estimates will be correlated with TB31F antibody measures to obtain the best possible fit for DMFA, DSF and SMFA separately. This will allow us to estimate IC50 and IC80 values for TB31F for each assay separately and model TRA and TBA estimates based on antibody concentration. TRA/TBA modeling is relevant because the precision of these estimates decreases with decreasing activity. Samples with lower levels of TRA (typically below 80%) and TBA may thus have relatively imprecise estimates. For some analyses, we may thus use TRA or TBA estimates that are inferred from antibody concentration based on the best fit model for the association between antibody concentration and TRA or TBA. For this fit, will use mixed effects models, similar to methods described by Miura et al. and Ramjith et al, adjusting TB31F antibody concentrations measured in serum to reflect whole blood concentrations. These models will estimate Inhibitory Concentration values (e.g. IC80, IC50) based on the best fit.

TB31F concentration in serum at which 80% TRA is expected (IC80) is calculated through (mixed-effects) linear regression by regressing the square root of serum concentration on the log-mean

oocyst ratio, i.e.  $IC_{80} = \left( \frac{\left( \log\left(\frac{100}{100-80}\right) - \hat{\beta}_0 \right)}{\hat{\beta}_1} \right)^2$  where  $\hat{\beta}_0$  and  $\hat{\beta}_1$  are the estimated regression coefficients

for the intercept and slope of the linear model respectively. The delta method will be used to estimate the standard error for the IC80 value and thus a 95% confidence intervals for the IC80 can be calculated. To compare assays (SMFA/DMFA/DSF) we can include a categorical variable in the model as an interaction variable to allow different slopes ( $\hat{\beta}_1$ ) to be estimated for the different assays.

Thereafter comparisons can be drawn for the IC80 values between assays. A similar calculation is made for IC50 values.

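### The delta-method interval for IC80 ignores that IC80 is a positive, squared ratio: its lower limit can fall below zero, and its upper limit tends to be too low when IC80 is poorly determined or extrapolated

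*SAP*

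**What the plan says.** In the SAP section on estimated inhibitory concentrations, IC80 is ((log 5 − b0)/b1)², where b0 and b1 are the estimates "for the intercept and slope of the linear model respectively". The regression is described as made "by regressing the square root of serum concentration on the log-mean" oocyst ratio. On uncertainty the section says "The delta method will be used to estimate the standard error for the" IC80 "value and thus a 95% confidence intervals for the" IC80. IC50 is to be calculated in a similar way, and IC80 values may be compared between SMFA, DMFA and DSF through an interaction term.

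No log or square-root scale is named for the interval, and no Fieller, profile or bootstrap method. The general rule is "Confidence intervals and P values will be based on 0.05 as significance level". The rule in the same section on transforming non-normal data concerns continuous outcomes, not a parameter derived from a fitted model, so it does not settle the scale.

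**The concern.** A concentration cannot be negative, and the square of a ratio of two estimates generally does not have a symmetric sampling distribution. An interval of the form estimate ± 1.96 SE on the concentration scale respects neither fact. Two faults can follow: a lower limit that cannot be reported, and an upper limit that stops short when the data determine IC80 weakly. The upper limit matters most to a reader, because it says how much antibody might be needed for 80% activity. The method serves IC80 and, by the similar calculation, IC50, for up to three assays.

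**Working it through.** **Inputs from the SAP.** The IC80 formula, with L = ln(100/20) = 1.609; two-sided 95%, z = 1.96; 30 + 30 = 60 participants on TB31F in the efficacy cohort (Table 3), or 2 × 20 = 40 if only those infectious at baseline are kept (Sample size); post-baseline feeds on days 1, 5 and 14 for DMFA (three) and days 1 and 5 for DSF (two). The SAP gives no expected IC80, slope, residual SD or SE, so it has no figure to reproduce, and every precision input below is an assumption.

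**Direction of the regression.** Taken literally, the SAP's wording makes root concentration the response. The formula instead solves a line in which the log oocyst ratio is the response. I follow the formula.

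**Delta interval.** Let r = (L − b0)/b1, with V00, V11 and V01 the variances and covariance of b0 and b1.

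- SE(r) ≈ √(V00 + r²V11 + 2rV01)/|b1|
- SE(IC80) ≈ 2|r|·SE(r)
- interval: r² ± 1.96 × 2|r|·SE(r)

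**Negative lower limit.** r² − 3.92|r|·SE(r) < 0 exactly when SE(r)/|r| > 1/3.92 = 25.5%, that is, when SE(IC80)/IC80 > 1/1.96 = 51%. This needs no assumption.

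**Effect of the square alone.** Squaring the limits of r ± 1.96 SE(r), when both are positive, raises both limits by 3.84·SE(r)² relative to the delta interval. In multiples of IC80:

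| Relative SE of IC80 | Delta limits | Squared limits of r |
|---|---|---|
| 20% | 0.61 to 1.39 | 0.65 to 1.43 |
| 50% | 0.02 to 1.98 | 0.26 to 2.22 |
| 60% | −0.18 to 2.18 | 0.17 to 2.52 |

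If r is normal, the truth lies above the delta interval in 3.8%, 5.6% and 7.7% of draws at relative SEs of 20%, 40% and 60%, and below it in 1.6%, 1.0% and 0.6%.

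**Ratio and square together.** 400,000 draws of (b0, b1) from a bivariate normal, assuming true b0 = 0 and b1 = 1:

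| Slope CV | SE(b0) | Correlation | Truth above | Truth below | Coverage | Lower limit < 0 |
|---|---|---|---|---|---|---|
| 10% | 0.1 | −0.7 | 4.9% | 0.2% | 94.9% | 0% |
| 20% | 0.3 | −0.7 | 5.9% | 0.0% | 94.1% | 2% |
| 30% | 0.5 | −0.7 | 6.9% | 0.0% | 93.1% | 46% |
| 10% | 0.3 | −0.7 | 3.9% | 1.6% | 94.5% | 1% |
| 10% | 0.3 | −0.9 | 2.5% | 2.8% | 94.7% | 0.4% |
| 20% | 0.5 | −0.95 | 1.6% | 3.9% | 94.5% | 12% |

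Fieller's interval covered 95.0–95.1% in all six rows. That is expected, since the draws meet its assumptions exactly.

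**The regression itself.** Simulated with a random intercept, 40 or 60 participants and 2 or 3 feeds each, 4,000 runs per scenario. Assumed: residual SD 0.5–1.5, intercept SD 0.5–1, log-SD of concentration 0.6 or 1.2.

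- *Median concentration 0.25–0.5 times IC80, log-SD 0.6:* coverage 83–95%, with 89–100% of misses on the upper side. In the least precise scenario 17% missed on that side. In one example with true IC80 = 2, the upper limit was 3.29 against Fieller's 6.38.
- *Median equal to IC80:* coverage 94.5–98%, with 51–80% of misses on the upper side.
- *Median 2–10 times IC80:* coverage 91–96%, with 28–78% of misses on the upper side. The upper limit is close to Fieller's and sometimes above it (2.64 against 2.61; 3.61 against 3.51).

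Negative lower limits occurred in 0% of runs in precise scenarios and in up to 68% in the least precise. Squared Fieller limits covered 94.4–95.9% throughout.

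**The case against.** The delta method is a standard large-sample choice, and the SAP never says that the interval must be symmetric. Total coverage in the bivariate draws stays at 93–95%. SMFA samples are to be chosen to inform IC80, which works against upward extrapolation in that assay. IC80 is listed among the exploratory objectives.

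A reader might infer that the upper limit is always too low and that nearly all misses fall on one side. The working does not support this. With a coefficient correlation of −0.9 the misses balance, at −0.95 they reverse, and concentrations that bracket or exceed IC80 share them between sides.

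A reader might also infer that the in silico dosing and duration work inherits this interval. The SAP bases that work on a separate non-linear mixed effects PK/PD model, whose parameter imprecision has its own method (the NONMEM covariance step or sampling importance resampling). Nothing there takes the IC80 limit as an input.

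These points stand and limit the concern. They do not remove it: the SAP names no other construction, the negative limit follows from algebra, and DMFA and DSF have no IC80-targeted sample selection like that described for SMFA. The SAP itself warns that activity estimates below about 80% tend to be imprecise.

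**Conclusion.** The point holds in conditional form. Read naturally, the interval has a negative lower limit whenever the relative SE of IC80 exceeds about 51%. Its upper limit tends to be too low when IC80 is poorly determined or lies above most of the measured concentrations: upper-side misses of about 4–7% in the bivariate draws, and up to 17% in the most extreme assumed regression setting, against 2.5% nominal. Elsewhere the interval performs acceptably. The sizes rest on assumed precision, correlation and concentration ranges, and the SAP cannot show which case the trial will meet. Because IC80 is exploratory, this is a worthwhile small improvement and does not threaten the trial's main conclusions.

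**What to change.** Replace the delta-method sentence. Form the 95% Fieller interval for r, the set of values satisfying (b1² − 3.84·V11)r² − 2[(L − b0)b1 + 3.84·V01]r + (L − b0)² − 3.84·V00 ≤ 0, and square its limits under two stated rules:

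- Set a negative lower limit to zero before squaring, since squaring it directly would give a spurious positive limit. With SE(b0) = 0.5 a negative Fieller lower limit arose in about 6–10% of draws.
- Report the upper limit as not estimable when the slope is not significant at the two-sided 5% level, because the Fieller set is then unbounded. This arose in about 9% of draws at a slope CV of 30%.

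Alternatively, use a percentile interval from a bootstrap that resamples participants. Treat IC50 in the same way, with log 2 in place of log 5. Compare assays on the log of the IC80 ratio. A participant-level bootstrap is the simpler route there, because Fieller's theorem covers one ratio of estimates and not, in general, a ratio of two such ratios. A delta interval on the log scale would keep limits positive, but in the regression runs it often moved the misses to the lower-limit side.

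The cost is a reworded sentence, a few more lines of code, and an upper limit that is wider or occasionally unbounded.

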#### **Efficacy outcome measures related to transmission reducing activity (reductions in oocyst intensity):**

We will determine averaged within-individual percent reduction in the density of oocysts at days post-treatment (1, 5, 14) compared to baseline (day 0) for each group. This will be assessed through DMFA, DSF and SMFA and outcomes for these different feeding assays will be presented separately as percentage reduction (with 100% as total reduction of transmission, and negative values as enhanced transmission) with 95% confidence interval. For DMFA and DSF, these data will be analysed for all individuals who received the product per protocol without restrictions to baseline infectivity, and for those individuals who are infectious at baseline (i.e. infecting at least one mosquito with any number of oocysts). For SMFA, these data will be analysed for all individuals who received the product per protocol without restrictions to baseline infectivity in DMFA or DSF, as well as for the subset of individuals who are infectious at baseline. SMFA, an exploratory outcome, will be conducted after unblinding to allow testing of a realistic sub selection of test and control samples. Participants may have naturally acquired TRA due to exposure to gametocytes prior to enrollment; SMFA on baseline samples will allow us to identify these individuals. Additional samples that are most informative for determining the IC80 will be selected based on the ELISA data and tested in the SMFA. For this, one person not involved in data analysis will be unblinded and select samples based on ELISA values and treatment arm.

All analyses on within-individual percentage reduction in oocyst density will use a mixed effects negative binomial regression model with day of follow-up and dose of TB31F as fixed effects. A random intercept will be added to models to allow for participant-level variations (i.e. intra-cluster correlation).

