### Outcome measures related to estimated inhibitory concentrations:

Transmission blocking activity (TBA, the reduction in the proportion of infected mosquitoes) and transmission reducing activity (TRA, the reduction in oocyst numbers/infection intensity) will be determined for DMFA and DSF separately. Baseline infection prevalence and intensity estimates will be used to calculate relative reductions in these transmission measures during follow-up. For SMFA experiments, TRA will be quantified as the relative reduction in oocyst intensity for test samples (one feeder per test sample) compared to pooled naïve serum controls (two feeders). Samples may be tested in one or two independent SMFA experiments.

TRA values for each participant and time-point will be estimated using mixed effect negative binomial regression models with random intercepts for each experiment to account for between experiments differences in oocyst intensity that is achieved in control experiments (SMFA) or baseline measurements (DMFA/DSF).

TBA values for each participant and time-point will be estimated using mixed effect logistic regression models with random intercepts for each experiment to account for between experiments differences in oocyst prevalence that is achieved in control experiments (SMFA) or baseline measurements (DMFA/DSF). Of note: for SMFA TBA estimates are deemed to be less informative than TRA estimates due to the design of these experiments that aim for high oocyst prevalence and density in control experiments.

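### The cross-assay IC80 comparison needs a term for natural activity before dosing: SMFA is referenced to naive serum, DMFA and DSF to the participant's own baseline

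*SAP*

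**What the plan says.** The relevant text is in the SAP's analysis section on estimated inhibitory concentrations, read with its section on transmission reducing activity.

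- **References.** For SMFA, "TRA will be quantified as the relative reduction in oocyst intensity for test samples" against pooled naive serum controls. For DMFA and DSF, "Baseline infection prevalence and intensity estimates will be used to calculate relative reductions in these transmission measures during follow-up".
- **Natural immunity.** The SAP expects it: "Participants may have naturally acquired TRA due to exposure to gametocytes prior to enrollment". Day-0 SMFA is planned to identify these participants. Elsewhere the SAP uses cuts at TRA above 50% and above 80%.
- **IC80 formula.** The SAP describes "regressing the square root of serum concentration on the log-mean" oocyst ratio and sets IC80 = ((log(100/(100 − 80)) − b0)/b1)², where b0 and b1 "are the estimated regression coefficients" for intercept and slope. IC50 is obtained similarly.
- **Fits.** Activity is related to antibody concentration "to obtain the best possible fit for DMFA, DSF and SMFA separately". For the assay comparison the model can "include a categorical variable in the model as an interaction variable to allow different slopes", and then "Thereafter comparisons can be drawn for the IC80 values between assays".

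The IC80 text states no term for activity before dosing. Stratification by natural immunity is written for the infected-mosquito analyses, as exploratory work.

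**The concern.** An IC80 for TB31F is normally read as the concentration at which the antibody itself gives 80% reduction. In SMFA as planned, a post-dose sample carries natural activity plus TB31F activity, and both are scored against serum that has neither. In DMFA and DSF, natural activity that is stable over follow-up and acts multiplicatively sits in both the baseline and the follow-up feed, so it largely drops out of the ratio.

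The three IC80 values then answer different questions. SMFA and DMFA could appear to need different concentrations even if TB31F worked identically in both. The SMFA figure would also not carry over to people without natural immunity.

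**Working it through.** The SAP gives no IC80 value and no prevalence or level of natural TRA, so there is no figure of its own to reproduce. The check applies its formula to stated assumptions.

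**Inputs**
- From the SAP: the formula, with target ln(100/20) = ln 5 = 1.609 for IC80 and ln 2 = 0.693 for IC50; the two references; the 50% and 80% cuts for natural TRA.
- Assumed: a share f of participants has natural TRA of level t and the rest have none; natural and TB31F activity add on the log scale; the true TB31F slope is the same in every assay and its true intercept is zero.

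**1. SMFA with its own intercept.** The mean log ratio at zero TB31F is b0 = f × ln(1/(1 − t)). With the slope unchanged, planned IC80 / TB31F-only IC80 = ((1.609 − b0)/1.609)².

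| Share f | Natural TRA t | b0 | IC80 factor |
|---|---|---|---|
| 0% | any | 0 | 1.00 |
| 10% | 50% | 0.069 | 0.92 |
| 20% | 50% | 0.139 | 0.84 |
| 40% | 50% | 0.277 | 0.69 |
| 20% | 80% | 0.322 | 0.64 |

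For IC50 the target is smaller, so the effect is larger: at 20% of participants with 50% TRA the factor is ((0.693 − 0.139)/0.693)² = 0.8² = 0.64.

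**2. Cross-assay model read literally: one intercept, assay-specific slopes.** Set the true IC80 to 4 (arbitrary units), so the true slope is 1.609/2 = 0.805. Take an SMFA shift of 0.28 (about 40% of participants with 50% TRA, the highest of the 50% scenarios above) and a DMFA shift of 0. Noise-free least squares on 50 equally spaced root-concentrations from 0.5 upwards gives a shared intercept of 0.14.

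| Top of root-concentration range | Slope SMFA / DMFA | IC80 SMFA | IC80 DMFA | Ratio |
|---|---|---|---|---|
| 3 | 0.873 / 0.737 | 2.84 | 3.98 | 0.71 |
| 4 | 0.856 / 0.753 | 2.95 | 3.81 | 0.77 |
| 6 | 0.839 / 0.770 | 3.07 | 3.64 | 0.84 |

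First row: ((1.609 − 0.14)/0.873)² = 2.84 and ((1.609 − 0.14)/0.737)² = 3.98, up to rounding.

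**3. The same data with separate intercepts.** SMFA: 4 × ((1.609 − 0.28)/1.609)² = 2.73. DMFA: 4.00. Ratio: 0.68. The shared intercept thus brings SMFA slightly closer to the truth and moves DMFA away from it (down to 3.64/4 = 0.91). It is not the source of the low SMFA value.

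**4. A mild case.** With 10% of participants at 50% TRA, the shared-intercept fit gives SMFA 3.67 to 3.75, DMFA 3.99 to 3.91 and a ratio of 0.92 to 0.96.

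**5. Direction of the gap.** Suppose infectivity also falls naturally after baseline by 24% (an assumption), equally at all post-dose feeds. This adds ln(1/0.76) = 0.274 to the DMFA log ratio, and its own-intercept IC80 factor becomes ((1.609 − 0.274)/1.609)² = 0.69. That equals the SMFA factor at 40% with 50% TRA, so the gap vanishes. A larger fall would reverse it.

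**The case against.** The case for leaving the plan as it stands has four parts.

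- **The shared intercept is inferred.** The sentence is permissive, does not exclude an assay main effect, and follows a promise of separate fits. A reader might infer that the SAP fixes one common intercept and that this makes the SMFA IC80 too low. The text does not fix it, and steps 1 and 3 show that the low SMFA value arises with separate intercepts as well.
- **The planned quantity can be legitimate.** The SAP's SMFA outcome is defined relative to experimental controls, and its objective concerns naturally infected people. Total activity in exposed people fits both. This stands, and is why the unadjusted figure should be kept. It does not justify comparing that figure with own-baseline IC80s from DMFA and DSF.
- **The reach is limited.** A reader might extend the point to all six inhibitory-concentration outcomes and to the in-silico dosing work. The formula is written for TRA (outcomes 28 to 30), with IC50 by the similar calculation. Outcomes 25 to 27 concern the proportion of infected mosquitoes, and the dosing work uses a separate non-linear mixed-effects model. Carry-over to either is not shown.
- **Random effects may help.** The per-experiment random intercepts are stated for estimating TRA and TBA values. The IC80 regression itself gives no grouping factor, so a participant random intercept is not ruled out. By itself, though, it would not remove average natural activity from b0.

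**Conclusion.** The point holds as a minor one. The references differ, natural TRA is expected, and no term for pre-dose SMFA activity is stated. An SMFA IC80 read as the effect of TB31F is therefore too low whenever natural TRA is present, and the comparison with DMFA and DSF mixes total with baseline-relative activity.

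The size depends on prevalences that the SAP does not give: 0.92 to 0.69 of the TB31F-only value for 10% to 40% of participants at 50% natural TRA, and 0.64 for 20% at 80%. These figures assume additivity on the log scale and an unchanged slope. If the cross-assay model is read literally, part of the error also passes to DMFA and DSF.

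A reader might conclude that SMFA must come out below DMFA and DSF. The documents do not support a certain direction: cancellation in DMFA and DSF needs stable, multiplicative natural immunity, and natural change in infectivity since baseline does not cancel.

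The IC80 objectives are exploratory, and the primary DMFA endpoint is unaffected. Because SMFA is run after unblinding, the adjustment is best written down beforehand.

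**What to change.** In the SAP's analysis section on estimated inhibitory concentrations:

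1. State that the cross-assay model has assay main effects (separate intercepts) as well as assay-specific slopes, and that each assay's own intercept enters the formula.
2. Add each participant's day-0 SMFA log oocyst ratio to the SMFA model, as an offset or covariate with a participant random intercept. Report IC80 and IC50 at zero natural TRA for the assay comparison. Step 1 of this list is not enough without this.
3. Keep the unadjusted SMFA IC80 as a second figure, labelled as total activity relative to naive-serum controls.

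The cost is SAP wording and one model term. Baseline SMFA is already planned; since only a sub-selection of samples is tested, the day-0 sample of every participant in the SMFA fit has to be among them. The downside is slightly wider intervals.
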